Potential enrollees will be provided a simple questionnaire regarding dietary habits. This will help the researchers understand individuals' nutritional intake, more specifically vitamin D sources. They will also be provided an informative page on vitamin D function and treatment for deficiencies. During the physical, each subject will have blood drawn and baseline serum 25(OH) vitamin D3 will be recorded. Supplemental vitamin D3 treatment will be given in 50,000 IU dosages once a week for 8 weeks following the initial examination. The prescription will be: Vitamin D3 50,000 IU oral capsule take 1 pill per week for 8 weeks. Subjects receiving supplemental treatment will then have vitamin D3 levels checked again at 8 weeks to ensure serum levels have risen. These values will be recorded. Should serum levels of vitamin D3 remain below the target value of 30 ng/mL, these subjects will be treated again following the same protocol as the primary treatment to ensure the levels rise. The subjects will then be followed throughout the course of the season, including all training activities, practices, and games.

Both deficient and normal subjects will be re-tested in January upon return from winter break. Subjects showing serum 25(OH) vitamin D3 levels below normal will be given supplemental treatment of 50,000 IU dosages once a week for 8 weeks. These subjects may have new or recurring deficiencies. Serum levels will be checked again following the end of treatment to ensure levels have risen. Any subject that was within normal ranges in the fall sports season that drops to deficient ranges will be treated with the same dosage as the primary treatment. Should their serum vitamin D3 levels fail to rise after 8 weeks, a secondary treatment will be administered following the same protocol as the primary treatment.

Throughout the seasons, any subject complaining of pain or injury to the lower extremity will undergo examination by the physician in order to positively diagnosis the injury. Each positively identified stress fracture will be recorded for that subject, and the appropriate treatment and rehabilitation will ensue. The lower extremity will be defined as any portion of the femur, tibia, fibula, and bones of the foot and ankle. Should an injury occur that does not

directly relate to a stress fracture or the lower extremity, the subject will remain in the study. However, these subjects will be included in a separate analysis.

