Data collected will include preliminary vitamin D3 serum levels, vitamin D3 serum levels in January, and vitamin D3 levels eight weeks post-supplementation. Additionally, should a stress fracture or other injury occur, the following information will be recorded: name of subject, team, date of injury, activity to cause injury, and location of injury. Each data point will be recorded on a spreadsheet and saved for final analysis. Each individual working on this study will be to date with all required CITI and HIPAA training. Only individuals directly involved with the study will have access to records for the subjects.

k) Confidentiality

Blood samples used for testing vitamin D3 levels will only be kept temporarily. Once each subject has been tested, serum levels will be recorded and samples will be disposed of following laboratory safe handling procedures. The data collected for each subject will be recorded. Any follow-up vitamin D3 tests will follow the same order. Only individuals directly working on the study will have access to the data collected. Personnel collecting blood samples for the vitamin D3 test will temporarily have access to the results for the specific subject being tested.

l) Provisions to Monitor the Data to Ensure the Safety of Subjects

Subjects in this study are only at minimal risk with regards to treatment and testing. Difficulties may arise during administration of vitamin D supplements and during blood sampling.

m) Withdrawal of Subjects

There are several circumstances that may require the subject to be withdrawn from the study without consent. Any subject that ceases activities and involvement with a given sports team will be withdrawn from the study. Likewise, if a subject develops an injury that is not within the parameters of the study will be withdrawn from the study. These injuries may include, but are not limited to, fractures to bones not defined as lower extremity, severe muscles strains that inhibit their ability to perform, ligament sprains or tears that are not directly related to bone strength in the lower extremity, and any other injury that requires the subject to stop sports related activities. Any subject that becomes pregnant during the study will be removed from the study.

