Should it be deemed necessary for a subject to be withdrawn without consent, the subject will be notified and will sign a form acknowledging their release. Any data collected from the subject prior to removal will be kept for partial analysis but will not be included in the final analysis with subjects completing the entire study. Subjects being removed from the study will stop receiving supplemental treatment as part of the study, but may continue if it is beneficial for any injury or health related condition that occurs. Subjects will still be under the supervision of physicians and athletic training staff.

8) Risks to the Subjects

Subjects in the study are being examined for occurrence of stress fractures in the lower extremities. The main purpose of the study is prevention of these injuries, however they are still likely to occur. Stress fractures are the primary injury of note related to this study. Stress fractures show a range of symptoms, from mild discomfort and tenderness to the region, to severe pain and the inability for the subject to function normally. Each injury will be treated individually in order to promote the quickest and safest recovery. Being a sports related study, other injuries and difficulties that may occur outside of the parameters of the study may include torn muscles, tendons, or ligaments, ligament sprains and muscle strains, meniscus tears, bone fractures above the lower extremities, concussions, bruising, dehydration, fainting during training or events, and heat stress. These injuries will be treated by appropriate personnel, but will not be applied towards analysis in the study.

Blood sampling in order to obtain serum 25(OH) vitamin D levels can impact subjects differently. The risks are minimal, but may include slight pain or discomfort, bruising, bleeding, dizziness, becoming light-headed, or fainting. However, blood tests are a normal part of medical treatment and these risks do not put the subject in danger. Supplementation of vitamin D is considered a safe treatment as long as dosages are monitored and adequate. Doses higher than necessary may lead the subject to experience weakness, headaches, dry-mouth, nausea, or other

discomforts. Several possible difficulties may arise from the increased serum calcium levels due to vitamin D. These include heart arrhythmias, kidney problems, and over-active parathyroid function. These problems are very minimal and are unlikely to occur.

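### The procedures section keeps an athlete with a non-study injury in the study, the withdrawal section removes the same athlete, and the 2015-16 analysis set depends on which rule is followed

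*Combined protocol and SAP*

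**What the plan says.** Three places in the combined protocol and SAP deal with injuries other than the study outcome.

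- **Section g) Procedures Involved, prospective part.** If an injury does not "directly relate to a stress fracture or the lower extremity, the subject will remain in the study". The next sentence adds: "However, these subjects will be included in a separate analysis". Neither the content of that analysis nor its relation to the main one is given.
- **Section m) Withdrawal of Subjects.** The rule is that "if a subject develops an injury that is not within the parameters of the study will be withdrawn from the study". Examples follow: "These injuries may include, but are not limited to, fractures to bones not defined as lower extremity", then severe strains that limit performance, certain ligament sprains or tears, and "any other injury that requires the subject to stop sports related activities". The section goes on to keep a withdrawn athlete's data for a partial analysis but not for the final one, and to stop supplementation as part of the study, though it may continue if beneficial. It adds: "Subjects will still be under the supervision of physicians and athletic training staff".
- **Section 8) Risks to the Subjects.** Similar wording is used for a wider list: "other injuries and difficulties that may occur outside of the parameters of the study may include torn muscles, tendons, or ligaments", running on to "concussions, bruising, dehydration, fainting during training or events, and heat stress". These are to be treated but not applied towards the analysis. The section does not order withdrawal.

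Section i) Statistical Analysis specifies a large-sample test of two proportions for aims 1 and 2. It does not say which enrolled athletes form the 2015-16 numerator and denominator.

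**The concern.** The same athlete is kept by one section and removed by another, and nothing else in the document decides between them. The choice determines three things: whether the athlete's later stress fractures count, whether the athlete is in the aim 1 and aim 2 denominators, and whether the January retest still applies. Capsules are given by each team's own training staff, so different teams could follow different sections in good faith.

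Aim 1 compares 2015-16 with earlier years taken from chart review. Section g applies the same inclusion and exclusion criteria to those records but describes no withdrawal step for them. Removing athletes for an injury that arises during follow-up may therefore alter only the 2015-16 group. That is selection after enrolment, and an uncontrolled before-and-after comparison has no protection against it.

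**Working it through.** **1. The rules side by side, for an athlete with a broken finger**

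| Question | Section g | Section m |
|---|---|---|
| In the study? | Remains | Withdrawn |
| Analysis | Separate, undefined | Partial only, not final |
| Fracture follow-up for the study | Continues | None specified after withdrawal |

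The fracture example in section m carries no severity qualifier, so the conflict does not depend on how serious the injury is. The two rules overlap without being identical: section m also reaches some lower-limb strains and sprains that section g does not clearly cover.

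**2. The plan's power figure**

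Inputs from section i: N1 = 200, N2 = 800, P1 = 0.04, P2 = 0.10, two-sided alpha 0.05, pooled Z test.

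- Pooled proportion = (200 × 0.04 + 800 × 0.10)/1000 = 0.088
- SE under H0 = √[0.088 × 0.912 × (1/200 + 1/800)] = 0.02240
- SE under H1 = √[0.04 × 0.96/200 + 0.10 × 0.90/800] = 0.01745
- Power = Φ[(0.06 − 1.96 × 0.02240)/0.01745] = Φ(0.923) = 0.822

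This matches the stated 0.8220, so the arithmetic of the table is not in question. Exact binomial enumeration of the same test gives 0.831.

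**3. How many removals the figure tolerates**

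Section c expects about 200 athletes, the power table uses 200, and no allowance for withdrawal is stated. With N2 held at 800 and 4% versus 10%:

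| Analysed in 2015-16 | Removed | Normal approximation | Exact |
|---|---|---|---|
| 200 | 0 | 0.822 | 0.831 |
| 190 | 10 | 0.802 | 0.812 |
| 189 | 11 | 0.800 | 0.811 |
| 188 | 12 | 0.798 | 0.812 |
| 183 | 17 | – | 0.801 |
| 182 | 18 | – | 0.799 |
| 180 | 20 | 0.780 | 0.794 |
| 160 | 40 | 0.729 | 0.747 |

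Power drops below 80% after 11 removals (11/200 = 5.5%) by the normal approximation and after 17 (8.5%) by exact enumeration. The removal counts are assumptions, since the documents give no injury or withdrawal rate.

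**4. Direction of any bias**

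Assume a true overall risk of 10% with no treatment effect, a fraction x withdrawn, and risk among the withdrawn r times that of the others. The retained proportion is 0.10/[(1 − x) + r·x]. At an assumed x = 0.20:

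- r = 2: 0.10/1.20 = 8.3%
- r = 1: 10.0%
- r = 0.5 (for example, less training load after injury): 0.10/0.90 = 11.1%

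If the injured athletes instead stay in the denominator but are observed for only half the risk period, the proportion is 0.10 × 0.80 + 0.05 × 0.20 = 9.0%. The sign depends on r, on which the documents are silent.

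**The case against.** The strongest reply is that section m is meant for serious injuries. It opens by saying that circumstances may require withdrawal, and several examples are limited to injuries that are severe or stop sport. That stands as a limit on scope. A reader might infer from section 8 that a bruise or dehydration triggers withdrawal. The text does not support this: that list is in the risks section and orders no withdrawal. The shared phrase shows only that the parameters of the study have no defined boundary.

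Second, if the separate analysis in section g replaces the main one, both sections take these athletes out of the main comparison, and the loss of numbers does not come from the contradiction. This is possible because the term is undefined. The sections would still differ on cohort membership, fracture follow-up and the January retest.

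Third, a reader might infer that removal makes the 2015-16 fracture rate look falsely low, or that power collapses. The first needs injured athletes to have higher later risk, and the result reverses at half the risk. The second needs high removal rates, for which the documents give no basis.

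Fourth, it would be too strong to say that later fractures in withdrawn athletes go unseen. Section g records all injuries per subject, and withdrawn athletes stay under the same staff. What is missing is a statement that fractures after withdrawal are counted.

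For aim 2, losses unrelated to vitamin D status mainly cost precision. They do not by themselves bias that comparison.

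**Conclusion.** The contradiction between sections g and m is certain and stands in the current text. At a minimum it covers any fracture outside the lower extremity. Following section m takes such athletes out of the final analysis, possibly on the 2015-16 side of aim 1 alone. Neither the direction nor the size of the resulting bias can be established from the documents.

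The one figure tied to the plan's own design is the narrow margin: about 11 removals in 200 (normal approximation) or 17 (exact) before power for 4% versus 10% falls below 80%. It assumes exactly 200 enrolled, 800 controls and removed athletes left out of the analysis, so it is a sensitivity check and not a forecast. The reason to act is that the analysis set for aims 1 and 2 is not determined by the plan.

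**What to change.** Reconcile sections g, m and 8 into one rule, and define the analysis set in section i:

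1. An injury other than a lower-extremity stress fracture does not by itself end study follow-up. Record it with its date.
2. Keep recording stress fractures to the end of the follow-up window for every enrolled athlete still on a study team.
3. Count these athletes in the main aim 1 and aim 2 proportions.
4. Turn the separate analysis of section g into a sensitivity analysis that leaves them out.
5. Leave the team-departure and pregnancy grounds in section m as they are.

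Whether supplementation continues after such an injury is a clinical matter. The document should state it once and consistently, apart from the follow-up rule.

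The cost is protocol wording. Sections g, h and j already record injuries for each subject, and section m keeps these athletes under the same physicians and trainers. The small downside is that some time at reduced training load will count as follow-up, which the sensitivity analysis helps to examine.

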Other than normal activities required for each sport, the main risk to each subject primarily involves taking blood samples. Although sampling is routine, there will still be risks of bleeding, bruising, dizziness, and possible infections. Allowing only trained individuals to take blood samples will minimize these risks. Any injury that occurs during a sports event or training activity will be handled accordingly by one of the physicians or athletic trainers on site. All injuries, regardless of nature, will be recorded per subject.

Blood samples will be tested for 25(OH) vitamin D levels using the order (Vitamin D 25-OH, Calcifediol Request). The data will be kept for each subject, day of recording, and level on an Excel spreadsheet. Any stress fracture reported will be listed on the same spreadsheet, along with the date of occurrence and severity, per subject.

Each team's athletic training staff will administer one vitamin D capsule to each team member once a week before a scheduled meeting or practice. This will help ensure every athlete takes the proper dosage, no dosages are skipped, and every week is accounted for. Athletes may still have decreased levels after the first course, and a second round of 8-week treatment will be administered. Should the second round of treatment fail to elevate vitamin D levels, the January test will confirm and treatment will continue. As many students leave to visit family during break, it will be rather difficult to monitor every athlete's levels during this timeframe.

Retrospective: The retrospective portion of the study will involve review of athletes of the same sports teams and inclusion/exclusion criteria from seasons up to four years ago. Review of previous athlete information will be drawn from electronic records kept by the athletic training staff, both electronic and hand-written records kept by the orthopedic staff, and any lab records retained at Palmetto Health. The information that will be obtained will include athlete demographics, their respective sports, stress fracture occurrences, and vitamin D levels if this was noted. The time period for the retrospective chart review will be from January 2010 through August 2015. The rate of stress fracture occurrence will be compared to the prospective treatment phase. It is important to note that individuals in the retrospective analysis will not have personal information reported, as the main purpose is to determine a baseline stress fracture rate.

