Analysis of the historic group will follow similar protocol as the recruitment of new subjects. Information from previous subjects will include including gender, age and sports team information. Additional information obtained will include stress fracture occurrence(s) and location, and vitamin D levels (if recorded).

h) Data and Specimen Banking

Data for each enrolled subject will consist of name, age, gender, ethnicity, and sports team. Any personal or private information collected will only be used during data analysis. This may contain information regarding menstruation, dietary habits, and previous pregnancies. Names and private information of subjects will not be released outside of personnel directly attached to the study, and they will not be included in the final study publication. Serum 25(OH) vitamin D levels for each subject will be recorded at the initial examination and 8 weeks following the beginning of treatment. Every injury diagnosis will be recorded per individual. There will be no blood sample banking after vitamin D levels are determined.

i) Statistical Analysis

Sample Size Justification

A power analysis was performed using PASS 2008 software on the research aim to compare the proportion of athletes that experience a stress fracture in those with normal vitamin D levels (either normal at baseline or treated by supplementation) compared to four previous years when this approach was not used. You can see that if the proportion of athletes experiencing stress fracture in the control group is 10%, then if the true reduction in the treated group was to 4% or less, we would have greater than 80% chance (power) in this study to achieve statistical significance in a test of the two proportions.

Two Independent Proportions (Null Case) Power Analysis

Numeric Results of Tests Based on the Difference: P1 - P2

H0: P1-P2=0. H1: P1-P2=D1<>0. Test Statistic: Z test with pooled variance

Power	Sample	Sample	Prop H1	Prop	Diff if H0	Diff if H1	Target Alpha
	Size Grp 1	Size Grp 2	Grp 1 or Trtmnt	Grp 2 or Control			
	N1	N2	P1	P2	D0	D1	
0.9946	200	800	0.0200	0.1000	0.0000	-0.0800	0.0500
0.9509	200	800	0.0300	0.1000	0.0000	-0.0700	0.0500
0.8220	200	800	0.0400	0.1000	0.0000	-0.0600	0.0500
0.6188	200	800	0.0500	0.1000	0.0000	-0.0500	0.0500
0.4048	200	800	0.0600	0.1000	0.0000	-0.0400	0.0500
0.2337	200	800	0.0700	0.1000	0.0000	-0.0300	0.0500
0.1224	200	800	0.0800	0.1000	0.0000	-0.0200	0.0500

Statistical Analyses

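### Withdrawn 2015-16 athletes, with any stress fracture already recorded, leave the final analysis; the historical control group has no matching rule

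*Combined protocol and SAP*

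**What the plan says.** Withdrawal of Subjects (section m) names three triggers, all of them events after enrolment:

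- leaving the team: "Any subject that ceases activities and involvement with a given sports team will be withdrawn from the study";
- another injury: "if a subject develops an injury that is not within the parameters of the study will be withdrawn from the study";
- pregnancy: "Any subject that becomes pregnant during the study will be removed from the study".

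A stress fracture is not itself a trigger. The same section then says: "Any data collected from the subject prior to removal will be kept for partial analysis but will not be included in the final analysis". The sentence goes on to limit the final analysis to subjects who complete the whole study. It makes no exception for a stress fracture already on record, and the partial analysis is not defined. Withdrawn athletes are not lost from view, however: "Subjects will still be under the supervision of physicians and athletic training staff".

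For the control group, the Retrospective part of Procedures Involved (section g) reviews "athletes of the same sports teams and inclusion/exclusion criteria from seasons up to four years ago". On data it says: "The information that will be obtained will include athlete demographics, their respective sports, stress fracture occurrences, and vitamin D levels if this was noted". The paragraph that follows adds age, gender and fracture location, and says the historic group is handled much as new subjects are recruited. Neither place gives a withdrawal or completion rule, or lists team departure, other injuries, pregnancy or fracture date.

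The Aim 1 analysis (section i) is a large-sample test of two independent proportions with a 95% confidence interval. It does not mention withdrawals.

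**The concern.** Aim 1 compares 2015-16 with earlier years. There is no randomisation, so the comparison depends on counting athletes in the same way in both periods. Under section m, the numerator and denominator for 2015-16 are conditional on finishing the season. The historical numerator and denominator are not.

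If athletes with a fracture withdraw more often than others, the 2015-16 proportion falls for a reason unrelated to vitamin D. That is possible, since the risks section says a stress fracture can leave an athlete unable to function normally, and such an athlete may later leave the team. If they withdraw less often, for instance because early leavers have had little time to fracture, the proportion rises. Either shift could be read as an effect of supplementation, or could hide one.

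In Aim 2 both groups are 2015-16 athletes under the same rule, so this asymmetry between periods concerns Aim 1.

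**Working it through.** **Inputs from the documents.** N1 = 200, N2 = 800, control rate 10%, treated rate 4%, two-sided alpha 0.05, pooled-variance Z test, stated power 0.8220 (section i). About 200 athletes are expected to enrol (section c), so enrolled is taken as equal to analysed.

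**Assumed inputs.** The documents give no withdrawal rates. Every rate below is an illustration.

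**1. Stated power.** With p̄ = (200×0.04 + 800×0.10)/1000 = 0.088:

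- SE0 = √[0.088×0.912×(1/200 + 1/800)] = 0.02240
- SE1 = √[0.04×0.96/200 + 0.10×0.90/800] = 0.01745
- Power = Φ[(0.06 − 1.96×0.02240)/0.01745] = 0.822

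This reproduces the plan's figure.

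**2. Shift in the analysed rate with no true effect.** Call an athlete with a stress fracture over the full season a case. Let wf and wn be the withdrawal rates of cases and non-cases, and let the true risk be 10%.

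- Analysed rate = 0.1(1 − wf) / [0.1(1 − wf) + 0.9(1 − wn)]
- Analysed N1 = 200 × [0.1(1 − wf) + 0.9(1 − wn)]

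For wf = 25% and wn = 10%: 15 cases among 15 + 162 = 177 athletes, or 8.5%. The last two columns give the chance of a significant result against 10% in 800 (normal approximation; nominal 0.025 in each tail).

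| wf | wn | N1 analysed | Rate | False reduction | False increase |
|---|---|---|---|---|---|
| 10% | 10% | 180 | 10.0% | 0.025 | 0.025 |
| 15% | 10% | 179 | 9.5% | 0.037 | 0.014 |
| 25% | 10% | 177 | 8.5% | 0.080 | 0.003 |
| 0% | 10% | 182 | 11.0% | 0.011 | 0.064 |
| 0% | 20% | 164 | 12.2% | 0.004 | 0.145 |

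Exact binomial enumeration gives similar values, for example 0.076 in place of 0.080 and 0.150 in place of 0.145.

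**3. Sensitivity to single counts.** Pooled Z test against 80/800:

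- Near the threshold: 12/200 gives p = 0.080. Dropping one case alone (11/199) gives 0.0497. If one non-case also goes (11/198), p = 0.052; 11/180 gives 0.104. Dropping two cases gives 0.030 (10/198), 0.051 (10/185) or 0.062 (10/180).
- Away from it: 20/200 gives p = 1.00, and 19/199 and 18/198 give 0.85 and 0.70. 8/200 gives 0.007, and 7/199 and 6/198 give 0.004 and 0.002. Dropping one or two cases changes no conclusion.

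**4. Power if only completers are analysed.** For 4% versus 10% with N2 = 800, the formula in step 1 gives 0.822 at N1 = 200, 0.780 at N1 = 180 (10% withdrawn) and 0.729 at N1 = 160 (20% withdrawn).

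**The case against.** **The historical group is already matched.** It has the same teams and the same inclusion/exclusion criteria, and is handled in a way similar to recruitment. Applying the exclusion for athletes recovering from a lower-extremity injury needs some injury information, and the extraction list is worded as what it will include, so it need not be complete. This stands in part: the old charts may hold the data. But these statements govern entry. None applies a post-entry withdrawal rule to past athletes.

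**One trigger is uncertain.** Section g (Prospective) keeps athletes whose injury is unrelated to stress fracture or the lower extremity in the study, with a separate analysis, whereas section m withdraws athletes with out-of-scope injuries. This stands. The passages conflict and must be reconciled. Neither clearly keeps these athletes in the main comparison, and the other two triggers are not contradicted.

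**Materiality is not shown.** All withdrawal rates are assumed. At 15% versus 10% the shift is 0.5 points and the total two-sided error is 0.037 + 0.014 = 0.051, close to nominal. The p = 0.0497 example is an edge case. This is fair, and it is why no direction or size is claimed. The unequal rule itself is in the text and does not depend on these figures.

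**The remedy has costs of its own.** Early leavers contribute incomplete exposure. If that removed 5% or 10% of events from both planned rates (3.8% vs 9.5%, or 3.6% vs 9.0%), power would be 0.796 or 0.768. This stands. The 0.822 holds only if 4% and 10% are read as rates among all eligible athletes, early leavers included. An end-of-season window also differs from the academic year named in Aim 1, although it matches the monitoring period in section e.

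**Conclusion.** The concern holds and should be fixed. Section m removes withdrawn athletes and their recorded fractures from the 2015-16 side of the powered comparison, and nothing planned does the same for the historical side. That much rests on the text alone.

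Whether it causes bias depends on whether cases and non-cases withdraw at different rates, which the documents do not say. Under the assumed rates, with no true effect, the analysed 2015-16 rate lies between 8.5% and 12.2% instead of 10%, so a spurious difference in either direction is possible. With equal withdrawal there is none. The stated power is computed correctly, but it makes no allowance for withdrawal: under the completers-only rule it falls below 80% at an assumed 10% withdrawal.

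**What to change.** 1. **Replace the exclusion in section m.** Suggested text: *All enrolled athletes who met the inclusion/exclusion criteria are included in the final analysis of Aims 1 and 2, whether or not they are later withdrawn. Every confirmed lower-extremity stress fracture in the routine athletic-training or medical records up to the end of the athlete's season, or until the athlete leaves the team, counts as an event. A completers-only analysis is a sensitivity analysis.* Aim 2 is covered so that both aims use one analysis set.
2. **Add a parallel rule for the historical group in section g.** Suggested text: *All athletes on the same team rosters who met the same inclusion/exclusion criteria at the start of the season are in the denominator, whether or not they completed the season, with events counted over the same window.* Bring two passages into line with this: the mention under Resources Available of a retrospective analysis of deficient athletes, and the academic-year wording of Aim 1.
3. **Add fracture date to the historical extraction list.** Section j already records it for 2015-16.
4. **Reconcile sections g and m** on the study status of athletes with other injuries.
5. **Restate power** if the completers-only rule is kept.

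**Cost.** This is mostly wording. The historical review needs rosters, fracture dates and a season-start eligibility check, which the shared entry criteria already imply. Consent must allow use of routine injury records after study withdrawal. N1 stays at about 200. The drawback is that early leavers count with incomplete exposure; the completers-only sensitivity analysis shows how much this matters on the 2015-16 side only.
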